# **Experimental theme**

Comparing the consistency of self-collected vaginal specimens versus physician-collected cervical specimens for high-risk human papillomavirus testing using the "Hygeia Touch Self Sampling Kit for Women"

# **Study purposes**

"Hygeia Touch Self Sampling Kit for Women" was created and commissioned by Hygeia Touch Inc. This kit includes a self-sampling swab developed for Oriental women. It is constructed of non-toxic and non-allergenic materials and can be used by you. Collect enough exfoliated vaginal cells to test for human papillomavirus. This is a single-use sterilizing product. It is simple to use and allows women to self-collection freely and comfortably. The collected specimens should be forwarded to a reputable laboratory at room temperature for high-risk HPV type testing. We intend to give an alternative for women who do not obtain regular cervical screening, raise the national cervical screening rate, and further lower the incidence of cervical cancer.

The trial will involve 1,200 women who will self-sample using a kit for high-risk HPV testing, and their results will be compared to cervical samples collected by physicians. The physician-collected samples will serve as the standard for evaluating the consistency of HPV typing results between the two methods. This kit is classified as a Class II medical device by the TFDA of the Ministry of Health and Welfare. If the results demonstrate strong consistency between self-sampling and physician testing, an application will be made to classify the kit as a Class 2 medical device for women's self-sampling of high-risk HPV types.

## A. Primary objective:

For the test group, the consistency (agreement) of whether there is high-risk HPV detected by using the samples obtained by the self-collection kit and the samples collected by the doctor.

#### B. Secondary objectives:

- 1. Determine if women can effectively perform self-sampling by following provided instructions or videos.
- 2. Assess the safety of testing, including evaluations by physicians and self-sampling.
- 3. Evaluate the success rate of self-sampling, consistency, and compare results among different groups.
- 4. Examine the correlation between HPV test results selected by physicians or self-sampling, and compare with smear and histopathological diagnosis results.
- 5. Evaluate satisfaction with self-sampling.

#### Duration

2019/12/1-2021/12/31

# Study design and methods

- A. The primary aim of this study is to compare the reliability of self-collected specimens versus physician-collected specimens in detecting high-risk HPV. This clinical trial is being carried out at multiple centers in Taiwan with laboratory technicians being blind of the sample sources.
- B. The trial aims to assess how well regular women can collect specimens using self-collection kits without professional assistance
- C. To ensure effective specimen collection by ordinary women, visual aids and pre-recorded audio and video materials will be provided for self-learning. Participants will then answer a questionnaire to verify the clarity of the instructional materials. Before HPV testing, the laboratory will verify the specimen's integrity by testing for beta-globin DNA.
- D. Subject inclusion procedures:
- 1. Eligible women who agree to participate will sign a consent form after receiving an explanation from the doctor.
- 2. Once the predetermined number of participants is reached, no further subjects will be enrolled, and the test results will be revealed and analyzed statistically.
- E. Sample collection procedure:
- 1. After obtaining consent, the study nurse will provide a coded self-sampling swab to each subject for self-collection. Cervical cell collection by the physician will follow routine procedures in the outpatient clinic. The self-sampling swabs are randomly coded to ensure blinding for laboratory test operators.
- 2. Physician examination:
- (1) Doctors use a cytological brush to collect cervical cells in accordance with medical routine during the outpatient clinic.
- (2) The specimens collected for examination will be kept by nurses and sent to the National Tsing Hua University laboratory.
- (3) Vaginal lavage or intravaginal medication should be avoided before specimen collection. Additional tests like smear examination or colposcopy may be conducted if necessary.
- 3. Self-sampling:
- (1) Subjects will receive a "HygeiaTouch Self-sampling Kit for Women" containing a sterile self-sampling swab and sample collection tube. They must read the instruction manual, watch an instructional video, and confirm their understanding by answering questions.
- (2) After self-sampling, subjects will place the swab in the collection tube and hand it to the study nurse.

- (3) When collecting self-sampled specimens from subjects, the study nurse asked the subjects to complete the self-sampling questionnaire in the case report form and provided assistance. After the subjects fill out the questionnaire, the research nurse will take back the case report form.
- (4) Subjects can self-sampling on the day of the outpatient clinic or thereafter, but no biopsy, medicine, surgery or any form of treatment is allowed between the subject's self-sampling and the doctor's sampling. The self-collected specimens are placed into the collection tube of the set and stored at room temperature. Specimens must be sent to the study nurse within one week of collection.
- F. Specimen number and test results:
- 1. Test work bag:
- (1) In order to facilitate the conduct of the trial and avoid confusion and errors, each subject will be assigned a trial work bag with a subject number on it according to the order of inclusion in the trial after signing the subject consent form.
- (2) The test work bag contains:
- ♦ 1 copy of "Libo cytological Brush (set)" for medical examination
- Self-sampling: 1 copy of "HygeiaTouch Self-sampling Kit for Women"
- ♦ 1 copy of subject consent form
- ♦ 1 case report form
- 2. Physician collects specimens:
- (1) When conducting outpatient examinations, doctors will use test work bags marked with subject numbers according to the order in which subjects are included.
- (2) The subject number has been marked with a sticker on the collection tube of each "Libo Libo cytological Brush (Set)".
- (3) This subject number is the specimen number collected by the doctor.
- (4) In the experimental laboratory, samples are examined for HPV typing, and the results will be shared with doctors for clinical purposes. These results will be given to patients and used as a benchmark for consistency comparison in the study.
- 3. Self-collected samples from subjects:
- (1) The serial number of the self-collected specimen has been marked with a sticker on the specimen collection tube of each "HygeiaTouch Self-sampling Kit for Women".
- (2) The self-collected sample number is a number obtained by random garbled calculation based on the sample number collected by the physician. This number cannot directly determine the correlation between the specimen collected by the physician and the specimen collected by the subject.
- (3) When the specimens are extracted and tested in the test laboratory, the test operators do not know the correlation between the specimens.
- (4) After the trial, the self-collected specimens will be unblinded and compared with the test

results of the specimens collected by the physician for consistency.

- G. Transportation and inspection of specimens:
- 1. The research nurse will deliver the collected specimens collected by doctors and self-collected specimens to the laboratory in National Tsing Hua University by express delivery at normal temperature for storage at  $-20^{\circ}$ C and DNA extraction of the specimens .
- 2. The extracted DNA of the specimen will be sent by frozen express to [name] Industrial Co., Ltd. for HPV typing testing.
- 3. The laboratory's specimen operations will continue with the coding on the collection tubes, and no additional coding will be performed.

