#### Statistical methods

This study is a multi-center, operator-blinded clinical trial in Taiwan . It mainly explores the consistency of self-sampling of the product and that of doctors . This trial will use the test results of samples collected by doctors as the standard and compare them with the HPV type test results

of self-collected specimens from the same subject to verify the HPV types in the samples collected by doctors and self-sampling. consistency.

A. The trial design uses the status of cervical precancerous lesions as a stratification variable. Five groups of subjects will be recruited according to the following proportions. It is expected to recruit a total of 1,200 subjects:

The 5 groups of subjects included in the study	Inclusion ratio	Estimated number of people to be included
1. Those with no abnormal smears or history of cervical lesions	10%	120 people
2. Those who have had mild smear or pathological tissue abnormalities within 3-12 months and need to undergo cervical smear follow-up	15%	180 people
3. Have had moderate to severe smear or pathological tissue abnormalities or cervical cancer, have undergone cone surgery, and are currently being followed	20 %	240 people
4. Those who have mild smear or pathological tissue abnormalities within 3 months and have not yet been treated	20 %	240 people
5. Those who have found moderate to severe smear or pathological tissue abnormalities or cervical cancer within 3 months and have not yet received treatment	35%	420 people
The total number of subjects expected to be included		1,200 people

Based on clinical research, it is estimated that the HPV positivity rates in the above five groups are (1) 10%, (2) 70%, (3) 50%, (4) 70%, and (5) 90% respectively. Based on the experimental design, under the stratified recruitment ratio, the overall HPV positivity rate is expected to be approximately 67%.

- B. According to the main evaluation indicators of the test, the consistency of this study is defined as:
- 1. HPV16, 18, 31, 33, 35, 39, 45, 51, 52, 56, 58, 59, 66, 68 are cancer-causing high-risk types. The agreement on detecting the presence of high-risk HPV between physician-sampled specimens and self-collected specimens is listed as the main purpose. Consistency is defined as follows:
- (1) The high-risk HPV test results are consistent (agree). The test results indicate that either of the above-mentioned high-risk HPV types is present in both cases or that neither of them has high-risk HPV types.

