## Statistical considerations

### Statistical design, methods and analysis procedures

A. This study is a multi-center clinical trial in Taiwan to test the blindness of operators . It mainly explores the consistency between self- testing of products and doctor -testing . In this experiment, the test results of samples collected by doctors will be used as the standard, and compared with the results of HPV type test of samples collected by the same subject to verify the consistency of HPV types in samples collected by doctors and self- sampled samples.

B. The experimental design uses the status of cervical precancerous lesions as a stratification variable, and the 5 groups of test groups are divided into the following proportions:

5 groups of subjects included in the subjects	Inclusion ratio
1. No history of abnormal smear or cervical lesions	10%
2. There have been mild smears or pathological abnormalities within 3-12 months, and those who need to receive Pap smear follow-up	15%
3. Those who have had moderate to severe smear or pathological abnormalities or cervical cancer, have received conical surgery , and are currently receiving follow-up	20 %
4. Mild smears or pathological tissue abnormalities within 3 months, who have not yet been treated	20 %
5. Moderate and severe abnormalities in smear or pathological tissue or cervical cancer found within 3 months, and those who have not received treatment	35%

According to relevant literature research, it is estimated that the positive probability of HPV in the five groups is (1) 10% , (2) 70% , (3) 50%, ( 4 ) 70% , ( 5 ) 90%, depending on the experimental design Under the stratum recruitment ratio , the overall HPV positive rate is expected to be about 67% , as shown in the table below .

Stratification	AI location rate	S stratified HPV positive prob.
1. No history of abnormal smear or cervical lesions	0.1	0.1
2. There have been mild smears or pathological abnormalities within 3-12 months, and those who need to receive Pap smear follow-up	0.15	0.7

3. Those who have had moderate to severe smear or pathological abnormalities or cervical cancer, have received conical surgery , and are currently receiving follow-up	0.20	0.5
4. Mild smears or pathological tissue abnormalities within 3 months, who have not yet been treated	0.20	0.7
5. Moderate and severe abnormalities in smear or pathological tissue or cervical cancer found within 3 months, and those who have not received treatment	0.35	0.9

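### Must the plan be changed because its coding is described as hiding which specimens belong together, and not which collection method was used?

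*Protocol*

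**What the plan says.** The protocol mentions the blind first in its design summary. Item A of Study design and methods has "laboratory technicians being blind of the sample sources". Item E.1 adds: "The self-sampling swabs are randomly coded to ensure blinding for laboratory test operators".

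Items F and G give the mechanics. The physician's tube carries the subject number, which follows the order of inclusion; F.2(3) says "This subject number is the specimen number collected by the doctor". The self-collection tube carries a number scrambled from it, and F.3(2) states the purpose: "This number cannot directly determine the correlation between the specimen collected by the physician and the specimen collected by the subject". F.3(3) describes the position at extraction and testing: "the test operators do not know the correlation between the specimens". Under G.3 the laboratory keeps the tube codes and "no additional coding will be performed".

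The protocol's Statistical methods section calls the study a "multi-center, operator-blinded clinical trial in Taiwan". SAP item A (Statistical design, methods and analysis procedures) has a garbled counterpart, "multi-center clinical trial in Taiwan to test the blindness of operators", which plainly means operator-blinded. SAP item D defines the blind in terms of the tester, the two specimens and the subject. SAP item E repeats the coding of protocol F.

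**The concern.** The trial compares two collection methods and calls itself operator-blinded. The sentence in item A just before the blinding clause contrasts self-collected with physician-collected specimens, so a reader may well take the undefined term to mean collection method. The procedure described does not deliver that.

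Three features suggest that an operator might be able to tell the method, at least at extraction:

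- The two specimens come in collection tubes from two different kits (F.2(2), F.3(1)).
- Physician specimens bear inclusion-order numbers and self-collected ones bear scrambled numbers, with no recoding in the laboratory (F.2(3), F.3(2), G.3).
- Physician results go to the doctors for clinical use, while the self-collected specimens are unblinded only after the trial (F.2(4), F.3(4)).

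If method were visible and operators handled or read one class of specimen differently, positivity in that class could shift, and kappa with it. A report that claimed masking of collection method would also claim more than the written procedure supports. The results are meant to support a device registration, so that claim could be challenged.

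**Working it through.** There is no figure to reproduce. The check sets every statement of the blind side by side and asks what each one masks.

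| Place | What is said to be masked |
|---|---|
| Protocol, Study design A | The source of the sample, undefined |
| Protocol E.1 | Not stated; only the self-sampling swabs are said to be randomly coded |
| Protocol F.3(2) | Pairing |
| Protocol F.3(3) | Pairing, at extraction and testing |
| Protocol, Statistical methods | Not stated |
| SAP item A | Not stated |
| SAP item D | Pairing on the most natural reading; the translated sentence could also be read as method |
| SAP item E | Pairing |

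That gives 1 statement about source, 4 about pairing and 3 that do not say: 1 + 4 + 3 = 8. The count is not firm, because SAP item D is ambiguous. With D set apart it becomes 1 + 3 + 3 + 1 = 8. Either way, every statement that comes with a mechanism (F.3(2), F.3(3), SAP E) is about pairing.

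**Do the passages contradict each other?** No. Item A can mean the subject from whom a tube came. That reading works only as a statement about pairing, since the physician's tube bears the subject number itself, and F.3 then explains it. A summary phrase that a later section makes specific is loose wording and not a conflict.

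**Is collection method visible?** The documents do not settle this. They give neither the tubes' appearance nor the format of the two number series. G.2 sends extracted DNA to a separate company for typing and does not say what container it travels in. The three features listed under the concern are suggestive but prove nothing.

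**Which masking does the endpoint need most?** The primary measure is kappa for the presence of any of 14 high-risk types. The most damaging failure would be an operator who sees one result and reads its partner to match, which would inflate kappa directly. That needs knowledge of the pairing, and the coding withholds it. An operator who knew only the method could not steer an individual pair toward agreement. A general tendency to treat one class differently could still move kappa, but the documents give no input for its sign or size, so I make no estimate.

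**What would a wording change alter?** Specimens: 1,200 × 2 = 2,400, of which 0 would be relabelled. The hypotheses (kappa at most 0.66 against above 0.66), the planning value of 0.72, the 80% power, the 0.05 level, the 1,049 required and the 1,200 recruited would all stay as they are. So would the valid-specimen analysis set.

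**The case for a change.** The best argument for acting is that it costs little and that the report must say what was masked. One clarifying sentence in the design summary would prevent an overclaim, and the term in item A is indeed never defined. E.1, the closest support for a wider blind, covers only the self-sampling swabs and does not name collection method. All of that stands as an editorial observation.

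It does not amount to a reason to amend:

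- Replacing item A with a pairing-only sentence would prejudge the question. If method was in fact masked, for example by similar tubes and number formats, the edit would remove a true statement.
- Defining the term in item A alone would leave E.1, the protocol's Statistical methods and SAP item A just as unspecific.
- Asking whether extraction staff are covered is unnecessary for the blind described, because F.3(3) names extraction as well as testing.
- Masking method through random codes on both tubes would be more than a wording change. It would touch F.2(2), F.2(3), F.3(2) and SAP item E, and the labelling itself, against a bias that nothing in the documents shows.

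**Conclusion.** No change to the plan follows. One undefined phrase in a translated design summary is broader than the procedure set out later, and the later sections give a workable account of the blind: operators cannot match a woman's two specimens, at extraction or at testing. Whether collection method was also hidden is left unstated. Those writing the report can describe the blind as protocol F.3 and SAP items D and E do, and claim masking of method only if the sponsor can say how it was achieved.

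The size is nil as far as the documents show: no effect on kappa, the significance level, power or the 1,200 subjects, and no specimen relabelled. Following the plan as written gives the same analysis and the same conclusion.

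This rests on two assumptions: that the coding is carried out as described, and that operators cannot reverse the scrambled number or see the link before unblinding. Evidence that operators knew the method and handled the two kinds of specimen differently would raise a separate question about conduct, which rewording item A would not answer.

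### The self-swab may be taken after the physician's cervical brushing, and neither document fixes the order of the two samples, requires it to be recorded, or analyses by it

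*Protocol*

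**What the plan says.** The timing rules are in the Protocol, Study design and methods.

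- **Physician sample.** E.1: "Cervical cell collection by the physician will follow routine procedures in the outpatient clinic". E.2(1): "Doctors use a cytological brush to collect cervical cells in accordance with medical routine during the outpatient clinic". Here the verb in E.1 means in accordance with, so the sentence does not place one sample after the other.
- **Self-swab.** E.1: after consent, "the study nurse will provide a coded self-sampling swab to each subject for self-collection". This says when the swab is given, not when it is used. E.3(4): "Subjects can self-sampling on the day of the outpatient clinic or thereafter".
- **Between the samples.** E.3(4): "no biopsy, medicine, surgery or any form of treatment is allowed between the subject's self-sampling and the doctor's sampling". The physician's own brushing is not on this list.
- **Time limit.** E.3(4): "Specimens must be sent to the study nurse within one week of collection". This runs from collection to hand-over and does not limit the gap between the two samples.
- **Aim.** Item B: "The trial aims to assess how well regular women can collect specimens using self-collection kits without professional assistance".

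The SAP (Statistical considerations, items D and E) says only that each woman gives two specimens and that they are coded so that the laboratory cannot pair them. SAP Tables 4 to 9 have no row for order or interval.

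**The concern.** The kit is meant to pick up cells already shed into the vagina; Study purposes puts it as "Collect enough exfoliated vaginal cells to test for human papillomavirus". The reference sample is taken by brushing cells off the cervix. When the swab comes second, the brushing may have changed what it can collect. Loosened cervical cells may be carried into the swab, or infected cells may have been removed. In intended use no physician has just brushed the cervix.

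Two results are exposed. The primary kappa pools all valid pairs whatever their order, and the self-sampling success rate (beta-globin positive specimens) pools all women. Both are meant to support use of the kit without a clinician. Coding the specimens blinds the laboratory but does nothing about order.

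**Working it through.** **1. Is a physician-first pair permitted?** The brushing takes place during the clinic visit (E.2(1)). A swab on a later day (E.3(4)) therefore follows it. A same-day swab may come before or after. So physician-first pairs are allowed, and their share is not given.

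**2. Inputs.** From the SAP: null kappa 0.66, planned kappa 0.72, positivity 0.67, alpha 0.05, power 80%, 1,049 pairs. Assumed here: equal margins of 0.67 for both samples before any order effect, and a one-sided test.

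**3. The plan's own figure.** Chance agreement Pc = 0.67² + 0.33² = 0.5578. With the full Fleiss-Cohen-Everitt variance, the SD of kappa is 0.8019 at 0.66 and 0.7410 at 0.72.

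n = [(1.645 × 0.8019 + 0.842 × 0.7410) / 0.06]² ≈ 1,049, which matches the SAP. The short SD formula printed in the SAP gives 1,064.

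**4. Table at the null.** Each discordant cell is 0.67 × 0.33 × (1 − 0.66) = 0.0752, or 78.9 of 1,049. Thus about 79 physician-positive women are missed by the swab.

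**5. Shift misses.** Move a share of that cell to or from the both-positive cell, and recompute Po, Pc and kappa = (Po − Pc)/(1 − Pc). For 20% of misses turned into detections (15.8 women, 0.0150):

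- Po = 0.8497 + 0.0150 = 0.8647
- self-positive margin = 0.6850
- Pc = 0.67 × 0.6850 + 0.33 × 0.3150 = 0.5629
- kappa = 0.3018 / 0.4371 = 0.690

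The chance of success is the simulated share of trials of 1,049 pairs in which (estimate − 0.66)/SE exceeds 1.645, using the full variance.

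| Change in swab misses, all pairs | Women | Po | Pc | Kappa | Chance of success |
|---|---|---|---|---|---|
| none | 0 | 0.8497 | 0.5578 | 0.660 | about 6% |
| 10% fewer | about 8 | 0.8572 | 0.5604 | 0.675 | 16% |
| 20% fewer | about 16 | 0.8647 | 0.5629 | 0.690 | 36% |
| 20% more | about 16 | 0.8346 | 0.5527 | 0.630 | under 1% |

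**6. What the pooled shares mean.** Only physician-first women can be affected, so pooled share = (fraction physician-first) × (effect in those women). With half the pairs physician-first, the 10% row needs a 20% effect among them (0.5 × 0.20), and the 20% row needs 40% (0.5 × 0.40).

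**7. The same size against the sponsor.** Start at the planned kappa of 0.72 and turn 16 concordant positives into swab misses. Po falls from 0.8762 to 0.8609, Pc is 0.5526, and kappa = 0.3083 / 0.4474 = 0.689. The chance of success falls from 82% to about 35%.

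**8. Scale.** The whole design difference, 0.66 to 0.72, is 1,049 × (0.1503 − 0.1238) ≈ 28 discordant pairs.

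**The case against.** **The mechanism is conjecture.** Nothing in the documents says that brushing sheds detectable cells into the vagina, or for how long. This stands. What the plan contains is an uncontrolled order, not a demonstrated bias.

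**The favourable direction is not privileged.** A reader might infer that the design inflates agreement. The documents do not support that: depletion is as open as carry-over, and the mirror case makes the trial less likely to succeed. Larger effects can be computed (30% and 40% of all misses rescued give kappa 0.706 and 0.722, and 61% and 83% success). With half the pairs physician-first, though, these would need 60% and 80% of the misses in those women to be rescued.

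**Order may in fact be recorded.** The study nurse handles a case report form when the self-sample comes back, and the form's fields are not in the documents. It can be said that neither document requires order to be recorded or analysed. It cannot be said that order is unknown, or that the two kinds of pair could never be separated afterwards.

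**Interference between samples was considered.** E.3(4) bars treatment between the samples, and E.2(3) advises against lavage and intravaginal medication beforehand. Neither rule covers the brushing.

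**Limiting the claim to self-first pairs would cost power.** This stands. After 10% loss, 1,200 × 0.9 = 1,080 valid pairs remain, so the set falls below 1,049 once more than 31 pairs (31/1,080 = 2.9%) are physician-first.

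**Fixing the order has its own limits.** Taking the self-swab first moves any order effect onto the reference specimen. It also leaves a physician-first row made up mostly of later-day swabs.

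**Conclusion.** The point holds as a gap in the procedure and the analysis. Physician-first pairs are permitted, they differ from the intended unaided use, and no rule or planned analysis deals with them. E.3(4) carries this; the E.1 sentence on routine collection does not bear on sequence.

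The size is illustrative. Under equal starting margins, 67% positivity and 1,049 pairs, a net change of about 8 to 16 women moves kappa from 0.66 to 0.675 or 0.690, and the chance of success from about 6% to 16% or 36%. About 16 women in the other direction give 0.630 and under 1%. The share of physician-first pairs, the effect in them and its sign are all unknown. No size can be put on the effect on the beta-globin success rate.

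The documents do not show that agreement will be inflated, nor do they justify replacing the primary analysis set with self-first pairs. The case for acting is that the design margin is only about 28 discordant pairs and the remedy is cheap.

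**What to change.** 1. **Protocol E.1 and E.3.** When both samples are taken on the clinic day, have the self-swab taken and handed over before the physician's sampling.
2. **Case report form.** Require date and time of both samples.
3. **Primary analysis.** Keep kappa on all valid pairs, so that the sample size basis is unchanged.
4. **SAP Table 4.** Add a pre-specified sensitivity analysis for self-first and physician-first women, giving kappa in valid pairs and the valid-specimen rate among all women sampled. State that the physician-first row will be mostly later-day swabs, so it mixes order with time gap and does not isolate an effect of brushing.

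Cost: protocol wording, the date and time fields, extra table rows and a slightly longer clinic visit, with no added visits or sample size. The self-first row may hold fewer than 1,049 pairs and then has less than the planned 80% power on its own, so it should be read as supportive.
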